3.2 Exclusion Criteria

- 3.2.1** Myeloid blast crisis of chronic myeloid leukemia (CML), unless patient is not considered candidate for tyrosine kinase inhibitor treatment.
- 3.2.2** Concomitant illness associated with a likely survival of <1 year.
- 3.2.3** Active systemic fungal, bacterial, viral, or other infection, unless disease is under treatment with anti-microbials and/or controlled or stable. Patients with fever thought to be likely secondary to leukemia are eligible. Known hypersensitivity to any study drug.
- 3.2.4** Known hypersensitivity to any study drug used in this trial.
- 3.2.5** Pregnancy or lactation.
- 3.2.6** Concurrent treatment with any other anti-leukemia agent.

4.0 EVALUATION AND COUNSELING OF PATIENT

The patient will be completely evaluated with a history, physical examination, diagnostic testing if necessary, and review of outside slides and records if available. The protocol will be discussed thoroughly with the patient and family (if present), with description of all known risks to the patient. Alternative forms of treatment will be presented as objectively as possible, and the risks and hazards of the study explained to the patient. Consent will be obtained using forms approved by the local Institutional Review Board (IRB).

5.0 SUBJECT REGISTRATION

To register, the attending physician involved in the care of the potential study participant must contact the Study Coordinator, and a copy of the signed consent form, a signed HIPAA authorization must be available and faxed to the study team (Fax Cover Sheet in APPENDIX E; [contact]). To complete the registration process, the PI, Fred Hutch/UW Study Coordinator or designee will assign a patient study number, register the patient on the study, and enter the patient into the Clinical Trials Management System (CTMS), OnCore. A complete, signed, study consent and HIPAA consent are required for registration.

6.0 TREATMENT PLAN

This study is a single-center, open-label randomized pilot study of lower-dose vs higher-dose G-CLAM for medically less fit adults with newly diagnosed AML or analogous myeloid neoplasms at the Fred Hutchinson Cancer Research Center/University of Washington/Seattle Cancer Care Alliance.

Study Overview

In this pilot study, patients meeting the inclusion/exclusion criteria and their primary oncologists are asked whether or not they would agree to participate in the randomized treatment assignment (APPENDIX D). Patients agreeable to randomization will be assigned in a 1:1 ratio to the higher-dose G-CLAM arm or the lower-dose G-CLAM arm that utilizes lower doses of cladribine, cytarabine, and mitoxantrone. For those who wish to not be randomized, the reasons to decline randomization will be recorded, and patients will be allowed to receive the treatment intensity of their choosing. Patients will receive higher-dose or lower-dose G-CLAM as follows:

Treatment arm	G-CSF (SC, D0-D5)	Cladribine (IV 2h, D1-D5)	Cytarabine (IV, D1-D5)	Mitoxantrone (IV, D1-D3)
Higher-dose G-CLAM	300 or 480 µg*	5 mg/m ²	2,000 mg/m ² **	18 mg/m ²
Lower-dose G-CLAM	300 or 480 µg*	2 mg/m ²	100 mg/m ² ***	6 mg/m ²

*Dosing based on patient weight: <76kg vs. ≥76 kg; **over 2 hours; ***over 1 hour

After study enrollment, patients will receive a first cycle of G-CLAM on one of the designated treatment arms. Post-induction bone marrows will be reassessed upon blood count recovery or between day Days +28 to +35 after start of chemotherapy, whichever occurs first. If a response other than a measurable (“minimal”) residual disease-negative (MRDneg) CR is achieved, the patient will receive re-induction with G-CLAM at the same dosing. Patients who achieve a morphologic CR or CR with incomplete count recovery (CRi) with up to 2 courses of higher-dose G-CLAM or up to 6 courses of lower-dose G-CLAM can receive consolidation therapy with G-CLA (i.e. mitoxantrone omitted; up to 4 cycles with high-dose G-CLA and up to 12 cycles of low-dose G-CLA).

6.1 Baseline/Pre-Treatment Assessment

The following procedures should be obtained at baseline before initiation of study therapy to establish trial eligibility and allow patient characterization and disease prognostication. Results of tests and/or procedures conducted as per standard of care may be used to determine study eligibility if conducted within an appropriate window prior to screening. Outside testing and previously collected clinical data may be used if within the appropriate time frame.

- 6.1.1** History and physical examination (assessed within 14 days prior to study day 0).
- 6.1.2** Bone marrow examination (or peripheral blood assessment if $\geq 10\%$ blasts are present) with morphologic and flow cytometric assessment. Routine cytogenetic analysis and molecular testing should be obtained. A bone marrow biopsy should be obtained if spicules are absent from the aspirate sample (aspirate and biopsy to be assessed within 2 months prior to study day 0).
- 6.1.2** Complete blood counts with differential blood count and platelet count (assessed within 14 days prior to study day 0).
- 6.1.3** Metabolic panel, including bilirubin, albumin, and creatinine (assessed within 14 days prior to study day 0).
- 6.1.4** MUGA scan or echocardiography, or other appropriate diagnostic modality, to assess left ventricular ejection fraction (LVEF; assessed within 3 months prior to study day 0).

6.2 Pre-Treatment

At the discretion of the treating physician for clinical management only, allopurinol 300 mg PO daily (or equivalent dose adjusted for renal function) may be considered in all patients without known allergies to allopurinol to reduce the risk of tumor lysis. Higher doses of allopurinol are permitted if patients develop tumor lysis syndrome. Patients may receive rasburicase, a recombinant uric acid oxidase, for the prevention and/or treatment of tumor lysis syndrome at the discretion of the treating physician if clinically indicated. All patients should be adequately hydrated and receive anti-emetics as necessary.

6.3 Administration of G-CSF, Cladribine, and Cytarabine Mitoxantrone on the Higher-Dose Arm: INDUCTION

- 6.3.1** For induction: The doses of the elements of G-CLAM chemotherapy will be as follows G-CSF 300 or 480 μ cg/ (based on weight <76 kg vs. ≥ 76 kg) daily subcutaneously daily on Days 0-5, Cladribine 5 mg/m^2 IV daily over 2 hours on Days 1-5, Cytarabine 2,000 mg/m^2 IV daily over 2 hours on Days 1-5, and Mitoxantrone 18 mg/m^2 IV daily over 60 minutes on Days 1-3.
- 6.3.2** The doses of all medications are calculated using the patient's actual weight.
- 6.3.3** Days 0 and 1 G-CSF may be omitted at physician discretion for WBC $>20,000/\mu\text{L}$, signs/symptoms of leukostasis, or acute symptoms felt related to their high-grade myeloid neoplasm.
- 6.3.4** All treatment is given as intent-to-treat; missed doses will not be made up.

6.3.5 No investigational or commercial agents or therapies other than those described herein may be administered with the intent to treat the patient's malignancy.

6.3.6 **If the patient has significant organ-specific dysfunction at baseline (e.g. abnormal liver or kidney function), dose reduction can be considered as described in section 6.8 at the physician discretion in conjunction with the oncology pharmacist.**

Outline Treatment Schedule: Higher Dose G-CLAM	
Day	Treatment
0	G-CSF 300/480 μ cg
1	G-CSF, Cladribine 5 mg/m ² , Cytarabine 2,000 mg/m ² , Mitoxantrone 18 mg/m ²
2	G-CSF, Cladribine 5 mg/m ² , Cytarabine 2,000 mg/m ² , Mitoxantrone 18 mg/m ²
3	G-CSF, Cladribine 5 mg/m ² , Cytarabine 2,000 mg/m ² , Mitoxantrone 18 mg/m ²
4	G-CSF, Cladribine 5 mg/m ² , Cytarabine 2,000 mg/m ²
5	G-CSF, Cladribine 5 mg/m ² , Cytarabine 2,000 mg/m ²
28-35 OR blood count recovery	Bone marrow assessment

6.4 Administration of G-CSF, Cladribine, and Cytarabine Mitoxantrone on the Lower-Dose Arm: INDUCTION

6.4.1 For induction: The doses of the elements of G-CLAM chemotherapy will be as follows G-CSF 300 or 480 μ cg/ (based on weight <76 kg vs. \geq 76kg) daily subcutaneously daily on Days 0-5, Cladribine 2 mg/m² IV daily over 2 hours on Days 1-5, Cytarabine 100 mg/m² IV daily over 1 hour on Days 1-5, and Mitoxantrone 6 mg/m² IV daily over 60 minutes on Days 1-3.

6.4.2 The doses of all medications are calculated using the patient's actual weight.

6.4.3 Days 0 and 1 G-CSF may be omitted at physician discretion for WBC $>20,000/\mu$ L, signs/symptoms of leukostasis or acute symptoms felt related to their high-grade myeloid neoplasm.

6.4.4 All treatment is given as intent-to-treat; missed doses will not be made up.

6.4.5 No investigational or commercial agents or therapies other than those described herein may be administered with the intent to treat the patient's malignancy.

Outline Treatment Schedule: Low-Dose G-CLAM	
Day	Treatment
0	G-CSF 300/480 μ cg
1	G-CSF, Cladribine 2 mg/m ² , Cytarabine 100 mg/m ² , Mitoxantrone 6 mg/m ²
2	G-CSF, Cladribine 2 mg/m ² , Cytarabine 100 mg/m ² , Mitoxantrone 6 mg/m ²
3	G-CSF, Cladribine 2 mg/m ² , Cytarabine 100 mg/m ² , Mitoxantrone 6 mg/m ²

4	G-CSF, Cladribine 2 mg/m ² , Cytarabine 100 mg/m ²
5	G-CSF, Cladribine 2 mg/m ² , Cytarabine 100 mg/m ²
28-35 OR blood count recovery	Bone marrow assessment

6.5 Assessment for Response after First Induction Course

A bone marrow aspirate should be obtained upon blood count recovery (i.e. ANC >1,000/µL and platelet count >100,000/µL) or between Days +28 to +35 after start of G-CLAM chemotherapy, whichever occurs first; a bone marrow biopsy need only be obtained during this procedure if spicules are absent from the aspirate sample.

- 6.5.1 Patients achieving an MRDneg CR: Patients are eligible to receive consolidation therapy with G-CLA (dosing as per section 6.6): up to 4 cycles on the high-dose arm and up to 12 cycles on the low-dose arm
- 6.5.2 Patients achieving a MRDpos CR or CRI: Patients are eligible for a second cycle of induction therapy using the same dosing guidelines as cycle 1 or may proceed to consolidation therapy with G-CLA as per 6.6, per discretion of treating attending.
- 6.5.3 Patients with persistent disease: Patients with persistent disease ($\geq 5\%$ blasts) are eligible for a second course of induction chemotherapy at the same dosing used in cycle 1 provided all non-hematologic toxicities have resolved to Grade <2. If they are not in CR or CRI after the 2nd induction course, they will be removed from the study.
- 6.5.4 Patients with persistent aplasia without evidence of disease after Day +49: patients will be removed from protocol.

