- 6.8.1 If a patient develops Grade ≥ 3 non-hematologic toxicity other than Grade 3 infections within 28 days from the last dose of G-CLAM, the next course of G-CLAM will be given once toxicity is \leq grade 2; doses for this course will be cladribine 4 mg/m² days 1-5, cytarabine 1,500mg/m² days 1-5, mitoxantrone 14 mg/m² days 1-3, and G-CSF dose unchanged. Assuming these doses are well-tolerated the first course of G-CLA will be administered at these doses, omitting mitoxantrone. If Grade ≥ 3 non-hematologic toxicity occurs again, there will be a further reduction in doses of cladribine to 3 mg/m² daily days 1-5 and cytarabine to 1,000mg/m² daily days 1-5 for the first cycle of G-CLA. Doses for subsequent courses of G-CLA will be discussed with the Principal Investigator.
- 6.8.2 Mitoxantrone: If the bilirubin concentration is $\geq 3 \times$ IULN, consider a dose reduction of mitoxantrone by 25-50% in consultation with the Oncology Pharmacist
- 6.8.3 Cladribine: If the serum creatinine exceeds 2.0 mg/dL and/or estimated creatinine clearance (calculated by Cockcroft-Gault) decreases to less than 50 mL/min during therapy, we will consider dose reduction in discussion with the Oncology Pharmacist.
- 6.8.4 Cytarabine: If the serum creatinine exceeds 2.0 mg/dL and/or estimated creatinine clearance (calculated by Cockcroft-Gault) decreases significantly during therapy, we will consider dose reduction in discussion with the Oncology Pharmacist.

6.9 **Dose Modifications of Chemotherapeutic Drugs for Subsequent Treatment Cycles for Low-Dose Arm**

Given the doses of the chemotherapy in this arm are already low, there will be no further dose reduction for toxicity. Also, doses do not need to be adjusted based on liver or kidney function. Decisions whether to proceed with further cycles of chemotherapy if \geq Grade 3 toxicity in cycle 1 will be made by the PI in conjunction with the treating physician.

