APPENDIX B: DOSE MODIFICATION TABLE

For patients who experienced \geq Grade 3 non-hematologic toxicities excluding neutropenic fever and infections during the first induction, the following dose reduction can be considered for the next course

High-Dose Arm

Drug	Dose Reduction #1	Dose Reduction #2
G-CSF	No change	No change
Cladribine	Cladribine 4 mg/m ²	Cladribine 3 mg/m ²
Cytarabine	Cytarabine 1,500 mg/m ²	Cytarabine 1,000 mg/m ²
Mitoxantrone	Mitoxantrone 14 mg/m ²	NA

Low-Dose Arm

No dose reductions required.

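### After Grade 3 or higher non-hematologic toxicity in cycle 1, the protocol words the higher-dose arm's second-induction dose in three inconsistent ways: unchanged, optionally reduced, or reduced

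*Combined protocol and SAP*

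**What the plan says.** Four places bear on the dose of a second induction in the higher-dose arm.

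- **Section 6.0 (Study Overview).** If the response is anything other than an MRD-negative CR, "the patient will receive re-induction with G-CLAM at the same dosing". No exception for toxicity is given.
- **Section 6.5 (response after the first course).** For an MRD-positive CR or a CRi, 6.5.2 says: "Patients are eligible for a second cycle of induction therapy using the same dosing guidelines as cycle 1", with consolidation as the alternative. For persistent disease, 6.5.3 says that patients "are eligible for a second course of induction chemotherapy at the same dosing used in cycle 1 provided all non-hematologic toxicities have resolved" to below Grade 2. Neither item refers to 6.8.
- **Section 6.8 (dose modifications, higher-dose arm).** The heading covers induction and later cycles. The opening sentence uses permissive wording for patients with Grade 3 or higher non-hematologic toxicity in the first induction (neutropenic fever and infections excepted): a reduction may be considered. Item 6.8.1 beneath it is worded as an instruction: "doses for this course will be cladribine 4 mg/m² days 1-5, cytarabine 1,500mg/m² days 1-5, mitoxantrone 14 mg/m² days 1-3".
- **Appendix B.** After such toxicity, "the following dose reduction can be considered for the next course". The first-step doses in its table match those in 6.8.1.

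**The concern.** A protocol should let the treating physician and the pharmacist arrive at the same dose from the same facts. Here, someone working from the response-assessment section is told to repeat the cycle-1 dosing. The sentence in 6.5.3 deals with recovery from toxicity, so toxicity was in view when it was written. Someone working from 6.8.1 is told to give reduced doses. Someone working from the opening of 6.8, or from Appendix B, is told that the choice is open.

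The patients concerned have a TRM score of at least 13.1 (3.1.3) and have just had severe toxicity, so the first stake is safety. The second is consistency of the intervention. The trial contrasts two treatment intensities in an open-label setting. If the re-induction dose varies with the section consulted, what the higher-dose arm received is less well defined. The effect can also carry forward, because 6.8.1 bases the first consolidation course on the reduced doses, while 6.6.1 starts from the induction dose level and allows a reduction.

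**Working it through.** The plan states no figure to reproduce. The check is a reading of the passages and a short dose calculation.

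**Step 1: define one patient to whom all the passages apply.** Take a higher-dose patient with persistent disease after cycle 1 and a Grade 3 or higher non-hematologic toxicity that is neither neutropenic fever nor infection, occurring within 28 days of the last G-CLAM dose and since resolved to below Grade 2. This patient meets the trigger in the 6.8 opening, in 6.8.1 and in Appendix B, and also meets the recovery condition in 6.5.3.

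**Step 2: confirm that 6.8.1 and 6.5.3 address the same course.** The next course in 6.8.1 contains mitoxantrone. Consolidation omits mitoxantrone (6.0, 6.6.1). The higher-dose arm allows at most two G-CLAM courses to reach CR or CRi (6.0, 10.1.4). After toxicity in cycle 1, the course in 6.8.1 can therefore only be the second induction.

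**Step 3: set the statuses side by side.**

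| Place | Second-induction dose for this patient | Pointer to 6.8 |
|---|---|---|
| 6.0 | Same as cycle 1 | None |
| 6.5.3 | Same as cycle 1 | None |
| 6.8 opening | Reduction optional | n/a |
| Appendix B | Reduction optional | n/a |
| 6.8.1 | Reduced doses, mandatory wording | n/a |

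Elsewhere the protocol does send the reader to 6.8: 6.3.6 for baseline organ dysfunction and 6.6.1 for consolidation. The phrase about dosing guidelines in 6.5.2 is looser. It could be read to bring in 6.3.6, but that item concerns baseline dysfunction, not toxicity in cycle 1.

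**Step 4: size of the gap.** The cycle-1 daily doses come from 6.3.1: 5 mg/m² of cladribine and 2,000 mg/m² of cytarabine for five days each, and 18 mg/m² of mitoxantrone for three days. The reduced doses are those in 6.8.1. Course total = daily dose × days; reduction = 1 − reduced dose / cycle-1 dose.

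| Drug | Cycle-1 dosing, course total (mg/m²) | 6.8.1, course total (mg/m²) | Reduction |
|---|---|---|---|
| Cladribine | 5 × 5 = 25 | 4 × 5 = 20 | 1 − 4/5 = 20% |
| Cytarabine | 2,000 × 5 = 10,000 | 1,500 × 5 = 7,500 | 1 − 1,500/2,000 = 25% |
| Mitoxantrone | 18 × 3 = 54 | 14 × 3 = 42 | 1 − 14/18 = 22% |

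G-CSF is unchanged.

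**Step 5: how many patients.** The documents do not give the share who have both qualifying toxicity and a second induction. The nearest figure is in section 1.0: of 62 patients given G-CLAM at the MTD, 3 (3/62 = 4.8%) needed two cycles to reach best response. That cohort was much fitter (median TRM score 2.85), and the figure does not count all second courses, so it is only indicative.

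**Step 6: which analyses depend on it.** The primary endpoint (14.3.1) is the proportion agreeing to randomization, which is settled before any treatment. The monitoring rules in 14.4 use MRD-negative CR but do not say whether it is assessed after course 1 or as best response over both courses.

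**The case against.** The strongest reply is that this is a default dose with a dose-modification section, which is an ordinary and coherent structure. The heading of 6.8 claims induction and later cycles, and its trigger is toxicity in the first induction. If 6.5.3 were unconditional, the G-CLAM doses in 6.8.1 would have no second induction to apply to after cycle-1 toxicity. Section 6.6.1 shows the same pattern openly: same dose level first, then a permitted reduction. Sections 6.0 and 6.5.3 also cover both arms, so same dosing may mean only that the patient stays at the assigned arm's level. Finally, 6.5.3 confers eligibility and does not compel treatment.

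Much of this stands. A reader might infer that the protocol prescribes two fixed, contradictory doses for the same patient. The documents do not support that, because 6.8.1 sits under a permissive opening sentence, Appendix B is permissive too, and 6.8 can be read as the exception to 6.0 and 6.5.3.

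The reply does not settle everything. Once 6.8 is taken as the exception, its own text still disagrees on whether the reduction is a choice or a requirement. Items 6.8.2 to 6.8.4 are worded as things to consider; 6.8.1 alone is worded as what will happen. The missing cross-reference also matters in practice, since 6.3.6 and 6.6.1 show that the protocol supplies one where it wants 6.8 applied.

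**Conclusion.** The point holds as an inconsistency in the status of the dose reduction. For a higher-dose patient re-induced after Grade 3 or higher non-hematologic toxicity, the protocol reads as same dose (6.0, 6.5.3), reduction optional (6.8 opening, Appendix B) and reduction required (6.8.1). The doses at issue differ by 20% to 25% per drug for that course. The text cannot be followed as written without choosing between passages.

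Its reach is limited. The number of patients is not stated and is probably small. The primary endpoint is untouched, and the comparisons of response and survival are exploratory and declared unpowered (14.3.2).

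A reader might also infer that the inefficacy and between-arm stopping rules are compromised. That is not shown. It would require second-course responses to count toward MRD-negative CR, which 14.4 does not state, and no change in any stopping decision has been demonstrated.

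The conclusion rests on the current wording alone, with no assumption about which dose was intended. It deserves correction on grounds of safety and consistent treatment.

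**What to change.** Reconcile 6.0, 6.5.2, 6.5.3, the opening of 6.8, 6.8.1 and Appendix B so that one statement governs the second-induction dose in the higher-dose arm after Grade 3 or higher non-hematologic toxicity. Within that statement, say plainly whether the reduction is optional or required, and use the same wording in 6.8.1 and Appendix B. Add a cross-reference to it from 6.0 and 6.5.3, as 6.3.6 and 6.6.1 already have. The clinical team decides which statement applies; no dose is proposed here.

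Two neighboring mismatches are separate but sit in the same sentences and can be reconciled at the same time. One is the recovery grade before the next course (below Grade 2 in 6.5.3, Grade 2 or lower in 6.8.1). The other is the infection exclusion (all infections and neutropenic fever in the 6.8 opening and Appendix B, only Grade 3 infections in 6.8.1).

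The cost is a wording amendment with IRB approval. It needs no extra patients or procedures and no change to the sample size or the analysis.

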6.6 Consolidation Therapy

After achievement of a CR/CRI (irrespective of MRD) with 1-2 courses of G-CLAM therapy, patients are eligible for post-remission therapy with G-CLA.

- 6.6.1 The treatment is identical to the induction course but without mitoxantrone (i.e. G-CSF, cladribine, and cytarabine, or “G-CLA” at same dose level as induction). If a patient had excessive toxicities (grade ≥ 3 non-hematologic toxicity excluding neutropenic fever and infections) during induction, a dose reduction can be considered as described in sections 6.8 and 6.9, as well as APPENDIX B.
- 6.6.2 Post-remission courses should start within 6 weeks of achieving CR/CRI once patients have recovered to \leq Grade 2 toxicities from the previous course of therapy.
- 6.6.3 Patients on the higher-dose arm can receive up to 4 courses of consolidation therapy.
- 6.6.4 Patients on the lower-dose arm can receive up to 12 cycles of consolidation therapy.
- 6.6.5 Patients can proceed to transplantation barring contraindications and if a suitable donor is available.

6.7 **Monitoring during/after Induction and Consolidation Therapy**

For patient monitoring, the following studies and study intervals are suggested and will be performed at the physician's discretion:

- 6.7.1 Complete blood counts with differential blood count, including immature cells/blast, and platelet count at least 2 times weekly until ANC >500/ μ L and then at least weekly until platelet count >100,000/ μ L.
- 6.7.2 Metabolic panel, including bilirubin, ALT/AST, and creatinine at least weekly until ANC >1,000/ μ L and platelet count >100,000/ μ L.
- 6.7.3 If patients develop signs or symptoms suggestive of cardiac dysfunction, LVEF should be assessed using the same method to evaluate baseline LVEF status (MUGA scan or echocardiography, or other appropriate diagnostic modality).

6.8 **Dose Modifications of Chemotherapeutic Drugs for Induction or Subsequent Treatment Cycles for Higher-Dose Arm**

For patients who have organ dysfunction at baseline—defined as a serum creatinine > 2.0 mg/dL or a bilirubin concentration is $\geq 3 \times$ IULN— or those who experienced \geq Grade 3 non-hematologic toxicities excluding neutropenic fever and infections during the first induction, a dose reduction can be considered as follows (see also APPENDIX B):

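### Sections 6.5.3 and 6.8.1 give conflicting instructions on a second induction course for a higher-dose patient with persistent disease whose Grade 3 or higher toxicity has improved only to Grade 2

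*Combined protocol and SAP*

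**What the plan says.** Section 6.5.3 governs re-induction for patients with 5% blasts or more after the first course, and is not limited to one arm. Such patients "are eligible for a second course of induction chemotherapy at the same dosing used in cycle 1". The section attaches a recovery condition to this: "provided all non-hematologic toxicities have resolved to Grade <2". The Study Overview in section 6.0 also describes re-induction as using unchanged dosing.

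Section 6.8 is titled "Dose Modifications of Chemotherapeutic Drugs for Induction or Subsequent Treatment Cycles for Higher-Dose Arm". Its lead-in says that for patients with organ dysfunction at baseline, or Grade 3 or higher non-hematologic toxicity during the first induction, "a dose reduction can be considered as follows". Appendix B also presents the reduction as an option. Section 6.8.1 then uses firmer wording. After Grade 3 or higher non-hematologic toxicity, other than Grade 3 infections, within 28 days of the last G-CLAM dose, "the next course of G-CLAM will be given once toxicity is" grade 2 or lower, and "doses for this course will be cladribine 4 mg/m² days 1-5", with reduced cytarabine and mitoxantrone as well.

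Two neighbouring rules help to fix the scope. Section 6.6.2 says "Post-remission courses should start within 6 weeks of achieving CR/CRI once patients have recovered to" Grade 2 or lower, but it concerns consolidation. Section 6.9, for the lower-dose arm, states no grade threshold: decisions on further cycles after Grade 3 or higher toxicity in cycle 1 "will be made by the PI in conjunction with the treating physician".

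**The concern.** The recovery threshold is a safety gate before a second intensive course. Patients are selected for a TRM score of at least 13.1 (section 3.1.3), so they are at high predicted risk of early death. If two sections set the gate differently for the same patient, treatment depends on which section staff consult, and following either one can be recorded as a departure from the other.

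There is also a possible link to the data. A second induction is a further chance of an MRD-negative CR, and section 14.4 uses that endpoint in the within-arm inefficacy rule and in the between-arm Fisher test. Uneven application of the gate could add noise to that count on the higher-dose arm.

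**Working it through.** The plan states no figure on this point, so the check is a comparison of the rules.

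**Step 1: do both sections cover the same course?** Section 6.8 expressly includes induction. Section 6.8.1 gives the next G-CLAM course a mitoxantrone dose. Consolidation under 6.6.1 is G-CLA, which omits mitoxantrone. The next G-CLAM course after course 1 is therefore a second induction. For a patient with persistent disease, that is the course governed by 6.5.3.

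**Step 2: which grades does each section admit?** Grade <2 in 6.5.3 admits Grades 0 and 1. Grade 2 or lower in 6.8.1 admits Grades 0, 1 and 2. For a higher-dose patient with persistent disease and a qualifying prior toxicity:

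| Current grade of that toxicity | Section 6.5.3 | Section 6.8.1 |
|---|---|---|
| 0 or 1 | Eligible, at the cycle 1 dose | Course given, at reduced doses |
| 2 | Not eligible | Course given, at reduced doses |
| 3 or higher | Not eligible | Course waits for recovery |

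The two sections disagree on whether to treat at Grade 2 only.

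**Step 3: who is in that row?** Four conditions must hold together:

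- the patient is on the higher-dose arm;
- the patient has persistent disease after course 1;
- there was a Grade 3 or higher non-hematologic toxicity that meets the 6.8.1 trigger;
- that toxicity is now at Grade 2.

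A toxicity that never exceeded Grade 2 does not trigger 6.8.1 and falls under 6.5.3 alone. Patients in MRD-positive CR or CRi fall under 6.5.2, which states no recovery threshold. Section 6.6.2 applies to a different type of course and does not conflict with either section.

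**Step 4: is the dose wording consistent?** For the same patient, 6.5.3 and the Study Overview say unchanged dosing, the 6.8 lead-in and Appendix B say a reduction may be considered, and 6.8.1 states reduced doses as what will be given. The threshold and the dose are therefore both unsettled, and neither section refers to the other.

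**The case against.** The strongest reply is that the two sections govern different treatments: 6.5.3 a repeat course at the cycle 1 dose, and 6.8.1 a reduced-dose course after severe toxicity. A different recovery threshold for each would then be coherent, and the optional wording of the 6.8 lead-in supports reading 6.8.1 as the terms of a reduced-dose option. This reading is workable, and the difference in dose is a real mitigating fact. But the protocol does not state it. Section 6.5.3 is the only eligibility rule for re-induction in persistent disease and mentions no reduced-dose route, and 6.8.1 is worded as an instruction.

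A second reply is that the less-than sign in 6.5.3 may be a less-than-or-equal sign lost in text extraction. That cannot be excluded without the source PDF. However, the less-than-or-equal sign survives in 6.6.2 and 6.8.1, and a greater-than-or-equal sign survives within 6.5.3 itself, so the text is taken as it stands. If the sign was lost, the threshold conflict disappears and only the dose wording needs attention.

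A reader might also infer a sizeable effect. Section 14.4 gives historical rates of 22% MRD-negative CR and 27% early death, which leaves 100% − 22% − 27% = 51% apparently due a second course. With an assumed 10% to 30% of those at Grade 2, that gives about 5% to 15% of the arm (0.51 × 0.10 = 0.051; 0.51 × 0.30 = 0.153). The documents do not support this:

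- The rates come from a different drug, CPX-351, and are not stated to be results after one course.
- The 51% includes patients in MRD-positive CR or CRi (6.5.2) and patients with aplasia without disease (6.5.4).
- The assumed share counts any Grade 2 toxicity, not Grade 3 or higher toxicity that has improved to Grade 2.
- In the G-CLAM series in section 1.0, 4 of 62 patients (4/62 = 6.5%) had resistant disease. Those patients were fitter (median TRM score 2.85), so this is no substitute estimate, but it shows how poorly the base is known.

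**Conclusion.** The inconsistency is real but narrow. For a higher-dose patient who meets the four conditions above, 6.5.3 withholds a second induction and 6.8.1 says it will be given, at doses that other parts of the protocol describe differently. The number of such patients is probably small and cannot be calculated from the documents. The conclusion rests on the less-than sign in 6.5.3 being as printed, and on the absence of any stated rule separating full-dose from reduced-dose re-induction.

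A reader might go further and infer that the trial's conclusions are at risk: an altered MRD-negative CR count could close an arm, and section 14.3.1 treats early closure of an arm as showing that randomization is not feasible. That path exists in principle, but no effect is shown. The primary endpoint is willingness to be randomized, which this gate does not touch directly. The inefficacy rule stops an arm only at 0 responders among 10, so an affected patient alters it only by being the arm's sole responder. Nothing in the documents sizes an effect on the Fisher comparison. The case for acting is clarity of a safety rule, not a demonstrated statistical bias.

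**What to change.** The clinical team should reconcile 6.5.3 with 6.8.1 so that it is clear which rule governs a second induction course after Grade 3 or higher toxicity on the higher-dose arm. The revision should cover three things:

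- the recovery threshold;
- the dose wording attached to it, including whether the reduction is optional or required, made consistent across the Study Overview, 6.5.3, the 6.8 lead-in, 6.8.1 and Appendix B;
- a cross-reference between 6.5.3 and 6.8.1.

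If separate thresholds for full-dose and reduced-dose courses are intended, the protocol should say so. The sign in 6.5.3 should first be checked against the source PDF. Section 6.6.2 needs no change on this account. Which threshold or dose applies is a clinical decision, and none is proposed here.

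The cost is a sentence or two in a protocol amendment, with no effect on sample size, error rates or the analysis.
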